3.2 SECONDARY ENDPOINTS

(1) Binary assessment of cuff closure

Cuff closure will be assessed by an independent surgeon at one and six weeks, as well as at six months. Surgeon visual assessment will grade vaginal cuffs as closed or not closed, or the surgeon may indicate that it was not possible to determine. As such, subjects who experience a dehiscence and are considered a failure in analysis of the primary study safety endpoint will be a failure in this secondary endpoint (lack of closed cuff at six weeks). However, subjects could fail this secondary endpoint without failing the primary study safety endpoint.

In cases in which a surgeon is unable to assess cuff closure, the most recent successful evaluation of cuff closure (including intra-operative evaluation) will be used; reason for inability to determine will be recorded. Fisher's Exact Test will be used to assess possible significance of a difference in cuff closure scores between test and reference groups.

(2) Binary assessment of cuff healing

Vaginal cuff healing will be visually assessed by an independent surgeon at six weeks and six months. Surgeon visual assessment will grade vaginal cuffs as healed or not healed, or the surgeon may indicate that it was not possible to determine. In cases in which a surgeon is unable to assess cuff healing, the most recent successful evaluation of cuff closure will be used. If no prior evaluation has established cuff healing, the cuff will be assumed to have not healed yet. Reason for inability to determine healing will be recorded. Fisher's Exact Test will be used to assess possible significance of a difference in cuff closure scores between test and reference groups. Additionally, healing will be characterized using a predetermined list of binary assessment questions, these will not be statistically compared, but serve to characterize individual healing scores.

(3) Comparison of implant passing rates

The percentage of subjects experiencing implant (either clip or suture) passing by six-weeks and six-months post-operative will be compared between test and control groups using Fisher's Exact Test.

(4) Frequency of implant passing events associated with an Adverse Event

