6.3 MEASURES TO MINIMIZE BIAS: RANDOMIZATION AND BLINDING

Variable block size randomization will be employed to assign a vaginal cuff closure method to each subject. At the time of enrollment and after confirmation of intraoperative eligibility, a subject will be randomly assigned treatment (cuff closure) with the test device (Zip-stitch™) or reference device (VICRYL™). This assignment will be provided via sponsor provided randomization envelopes broken down in 2:1 variable block sizes and stratified by site. Treatment allocation blocks will vary from three to six subjects and will be split 2:1 test to reference assignment. This method helps safeguard against a simple randomization generating a smaller than intended test or reference group.

Subjects will be blinded to the cuff closure method they receive during surgery. Because operating surgeons cannot be blinded to the treatment they are providing, this trial cannot be completely double-blinded. Every effort will be made to minimize bias in post-operative data collection. Data collection will be performed by an investigator without access to the blinded to treatment assignment. Treatment assignment will be recorded at the time of procedure in the electronic data capture system. After this point, the investigator collecting follow-up data will be blinded to medical records and treatment group. The operative surgeon cannot be blinded as the performed treatment. They will be available during follow-up as needed but will not participate in data collection for patients that they provided treatment.

Database lock and data un-blinding will take place after completion of the last six-week follow-up visit. Subjects will still participate in the 6 and 12-month visit and extension period call, but data will be unblinded. The data collected at the 12-month telephone visit are limited to pain, dyspareunia, and adverse events. Adverse events are likely to have significant clinical sequelae, and therefore not likely to be forgotten. Pain and dyspareunia are evaluated based on experience in the time frame of the call, and therefore are not affected by recall bias.

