6.5.1 RESCUE TREATMENT

In the event that a subject is enrolled, and a random treatment is assigned, but the surgeon is unable to achieve cuff closure with the assigned cuff closure method, the surgeon may close the cuff using an alternate method. This event would be considered a protocol deviation and these subjects will be included in analysis of the primary efficacy outcome. These subjects will also be included in secondary endpoint ITT and safety populations, and subject safety data will be included in study analysis.

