 transition to laparotomy, surgeon's decision to close the cuff using suture with or without
 robotic assistance, realized subject satisfaction of exclusion criteria, or other complications.
- Investigator or coordinator will complete the Intra-Operative Screening Form during the procedure to confirm subject enrollment or exclusion.
- Once a subject has been enrolled, the subject will be assigned to a study group according to study randomization strategy.

Surgery - Cuff Closure

- Following intra-operative study enrollment, surgeon will close the cuff according to the subject's assigned study group.
- Surgeon will visually confirm the integrity of achieved vaginal cuff closure.
- The laparoscopic surgical video will be collected for reference.
- An investigator or coordinator will complete the Intra-Operative Report form and ensure surgeon evaluates cuff closure integrity and that laparoscopic video is saved.

One Week In-Person Follow-Up Visit

- This in-person follow-up visit should take place 7 ± 3 days of the study procedure and will include a vaginal examination for visual assessment of cuff closure.
- The subject will be assessed for study endpoints including implant passing, cuff closure evaluation, adverse events, pain, and dyspareunia.
- An investigator or coordinator other than that which provided cuff closure treatment will collect information for completion of case report forms by site coordinators as indicated in the SoA.

Six Week In-Person Follow-up Visit

This in-person follow-up visit should take place within six weeks ± five days of the study
procedure and will include a vaginal examination for visual assessment of cuff closure and
healing.

- Protocol QD-PRO-045 Rev 005
 - The subject will be assessed for study endpoints including implant passing, cuff closure and healing evaluation, adverse events, pain, and dyspareunia.
 - An investigator or coordinator other than that which provided cuff closure treatment will collect information for completion of case report forms by site coordinators as indicated in the SoA.

Six Month In-Person Follow-up Visit

- This in-person follow-up visit should take place within six months ± one week of the study procedure.
- The subject will be assessed for study endpoints including implant passing, cuff closure and healing evaluation, adverse events, pain, and dyspareunia.
- There will be a visual inspection of the vaginal cuff at this visit. An investigator or coordinator

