9.4.10 MISSING DATA & DATA IMPUTATION

Because implant passing is expected to be spontaneous, missing data will not be imputed for analysis of the primary study endpoint. Instead, if a subject is lost to follow-up prior to their six-week in-person visit, they will be included in the ITT population, but any incomplete data collection will be excluded from the total population evaluated for the primary study endpoint. For example, completed one-week follow-up data from a subject lost to follow-up between their one and six week visits will be included, but the uncompleted six-week data will be excluded, and they will not be included in the efficacy endpoint population totals for uncompleted follow-up timepoints. Data may be imputed based on existing data averages for subjects lost to follow-up after their six-week visit as part of additional study analysis, such as the 12-month unblinded follow-up reporting.

Sensitivity analysis will be performed on ITT population evaluation of the primary endpoint where all missing data are imputed as successes and separately as failures. Results of these analyses will be presented alongside primary endpoint evaluation. Every effort will be made to minimize missing data.

Additionally, any cases of vaginal cuff closure performed with a rescue method in accordance with protocol Section 6.5.1 will have their primary endpoint value set to missing. Their values will be imputed using multiple imputation. Additional information will be provided in the statistical analysis plan (SAP). These cases will also be included in sensitivity analysis determining possible effect of exclusion of these subjects from primary endpoint analysis.

Data imputation may be performed for appropriate secondary endpoints. Imputation will only be performed for secondary endpoints evaluating, or based on evaluation of, a status (as opposed to an incidence) and if a subject is lost to follow-up *after* their six-week visit. Data for subjects lost to follow-up before their six-week visit will not be imputed. Secondary endpoints that may allow for data imputation include (1) status of cuff closure, (2) status of cuff healing, (6) change in dyspareunia, and (7) change in pain.

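### A cuff that cannot be graded may take its closure value from the unblinded operating surgeon, so it is scored closed in practice at one week and, on one reading, at every visit

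*Combined protocol and SAP*

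**What the plan says.** Section 3.2, endpoint (1), sets the assessor: "Cuff closure will be assessed by an independent surgeon at one and six weeks, as well as at six months". It allows a third grade besides closed and not closed, since "the surgeon may indicate that it was not possible to determine". For such a cuff, "the most recent successful evaluation of cuff closure (including intra-operative evaluation) will be used", and the reason is recorded.

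The intra-operative evaluation is described in Section 8.1: "Surgeon will visually confirm the integrity of achieved vaginal cuff closure". Section 6.3 concedes that "The operative surgeon cannot be blinded as the performed treatment" and keeps that surgeon out of data collection on the women he or she treated. Under Section 6.5.1, if the assigned method does not achieve closure, "the surgeon may close the cuff using an alternate method".

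The neighbouring healing endpoint in Section 3.2 also carries a previous evaluation forward, but ends differently: "If no prior evaluation has established cuff healing, the cuff will be assumed to have not healed yet".

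Section 9.4.4 defines success for closure, at each timepoint, as a test failure rate no higher than the reference rate, and does not mention the carry-forward. Section 9.4.10 confines imputation of secondary endpoints to status endpoints in women lost after the six-week visit: "Data for subjects lost to follow-up before their six-week visit will not be imputed". Its all-success and all-failure sensitivity analysis covers the primary endpoint only.

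**The concern.** The intra-operative grade is a poor substitute for a follow-up grade. It comes from the person whose work is being judged, who knows the treatment. It also predates any event the endpoint is meant to detect, and because another closure method may be used it will be closed in practically every woman. Using it turns an examination that gave no answer into a success.

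The failures at risk are the ones this endpoint adds. A dehiscence needing re-operation is counted as a failure here in any case, so the rule acts on cuffs that are not closed but are not re-operated. The objectives table in Section 3 calls closure a fundamental evaluation of efficacy. Its success criterion compares two small observed proportions with no margin, and no planned analysis would show how far the result depends on the rule.

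**Working it through.** **Inputs.** The arms are 39 test and 20 reference (Sections 4.1 and 9.2). The criterion is a test failure rate no higher than the reference rate (Section 9.4.4). The test is a two-sided Fisher's exact test at 0.05 (Sections 1.1 and 9.4.4). Section 9.4.4 words the comparison as one of dehiscence; I take it as closure failure, in line with Section 3.2 and the acceptance criterion. The documents give no number of unassessable cuffs, so every such count below is assumed.

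**Plan's own figure.** 35/0.9 = 38.9, rounded up to 39 test. 39/2 = 19.5, rounded up to 20 reference. Total 59, as stated. The plan states no figure for the carry-forward rule.

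**Which value the rule picks up.** *Successful* may mean an evaluation that could be completed (A) or one with a closed result (B).

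- One week: the intra-operative evaluation is normally the only earlier one. The cuff is scored closed in practice under A and B.
- Six weeks and six months, reading A: the last completed grade is used, normally one from the independent surgeon, and it may be not closed. The intra-operative value returns only if no post-operative grade exists.
- Six weeks and six months, reading B: the rule looks back for a closed result. A woman graded not closed at one week and unassessable at six weeks could be scored closed at six weeks from the operating room.

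**Effect on the criterion.** Pairs are test, reference. The carry-forward is taken to give closed.

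| Observed failures | Unassessable | Rule as written | Excluded | Counted as not closed |
|---|---|---|---|---|
| 0, 0 | 1, 0 | 0/39 v 0/20: met | 0/38 v 0/20: met | 1/39 = 2.6% v 0%: not met, p = 1.00 |
| 0, 0 | 4, 0 | 0/39 v 0/20: met | 0/35 v 0/20: met | 4/39 = 10.3% v 0%: not met, p = 0.29 |
| 1, 1 | 1, 0 | 1/39 = 2.6% v 1/20 = 5.0%: met | 1/38 = 2.6% v 5.0%: met | 2/39 = 5.1% v 5.0%: not met, p = 1.00 |
| 0, 0 | 1, 1 | 0/39 v 0/20: met | 0/38 v 0/19: met | 1/39 = 2.6% v 1/20 = 5.0%: met, p = 1.00 |
| 0, 0 | 2, 1 | 0/39 v 0/20: met | 0/37 v 0/19: met | 2/39 = 5.1% v 1/20 = 5.0%: not met, p = 1.00 |

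With no observed failures, *t* unassessable test cuffs and *r* unassessable reference cuffs, counting them as not closed breaks the criterion when t/39 > r/20, that is t > 1.95r.

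**Effect on Fisher's test.** With no reference failures, 7/39 gives p = 0.083 and 8/39 (20.5%) gives p = 0.042. At 35 v 18 after 10% loss, 7/35 gives p = 0.081 and 8/35 gives p = 0.040. Eight unassessable test cuffs, all counted as failures, would be needed.

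**Effect on the failure rate.** If a share *u* of cuffs is unassessable and a share *q* of those is truly open, scoring them closed understates the failure rate by u × q. Over an assumed range:

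- 0.05 × 0.05 = 0.25 points
- 0.10 × 0.50 = 5 points
- 0.20 × 1.00 = 20 points

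**The case against.** A reader might infer that the rule turns all missing closure data into successes by construction. The documents do not support that. The rule is triggered by a grade given at an examination. Women without data leave the denominator under Section 9.4.1, and secondary endpoints are not imputed for loss before six weeks under Section 9.4.10. A known dehiscence stays a failure. At later visits the claim holds only under reading B. Reading A is the more natural, because the word follows a clause about being unable to assess, and because the healing paragraph uses the same phrase and then asks separately whether healing had been established.

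Three further points are fair:

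- A cuff starts closed and starts unhealed, so the opposite fall-backs for closure and healing have a logic and are not a contradiction.
- Excluding unassessable cuffs leaves the main result almost unchanged, as the table shows, so replacing the main rule does little by itself.
- The endpoint is labelled exploratory in the synopsis and is unpowered under Section 9.2. Reasons are recorded and individual data are listed under Section 9.4.9, so affected cases could be found afterwards.

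All of this narrows the point but does not remove it. At one week the choice of reading makes no practical difference. The intra-operative value remains an allowed source that runs against the independent assessment Section 3.2 sets up. The term is undefined, and no planned sensitivity analysis covers the endpoint.

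**Conclusion.** The concern holds in a limited form. An unassessable cuff is scored closed in practice at one week, and at every visit if *successful* means a closed result. One such test cuff can decide the acceptance criterion: 0% v 0% as written, against 2.6% v 0% if it counts as not closed. Fisher's test would rarely change.

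This rests on assumed counts of unassessable cuffs and on the inference, from the timing of the evaluation and the option of another closure method, that the intra-operative grade is almost always closed. The documents show no bias towards either arm; the rule lowers the failure rate in whichever arm has unassessable cuffs that are truly open.

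A reader might size the loss against a failure rate of 5%. The 5% figures in the protocol are an upper reported incidence of dehiscence and the implant-passing target, and neither is a closure-failure rate for this endpoint. The share of unassessable cuffs that are open has no source either, so only the range above can be given. The change is worth making, but the primary endpoints are untouched.

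**What to change.** 1. In Section 3.2(1), delete the parenthesis that admits the intra-operative evaluation.
2. Define a successful evaluation as a completed post-operative grade by the independent assessor, whether closed or not closed, and allow only such grades to be carried forward.
3. Treat a cuff with no such grade as missing.
4. Add a sensitivity analysis that counts every unassessable cuff as not closed. This step matters most, because exclusion alone leaves the result nearly unchanged.
5. Report the number of unassessable cuffs, with reasons, by arm and visit.
6. State the same rule in Section 9.4.4, and say in Section 9.4.10 how it stands beside the limit on imputing secondary endpoints.

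The cost is wording and one table. The reasons are already collected, so no new data are needed. The reported closure rate may look slightly less favourable.

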9.4.4 ANALYSIS OF SECONDARY EFFICACY ENDPOINTS

Secondary Endpoint (1) Cuff closure (compared between test and reference groups) will be assessed (yes or no) by an independent surgeon at one and six weeks, as well as at six months.

Data collection: Surgeon will visually assess vaginal cuff closure, indicating whether the vaginal mucosa is intact. If the vaginal cuff closure is determined not to be intact, then failure of this study endpoint will be indicated and the subject will be included in the ITT population for remaining study endpoints. If additional surgical intervention is necessary to address lack of cuff closure, follow-up will restart following the new procedure date. In this circumstance the new follow-up schedule will be included in the evaluation of remaining efficacy endpoints in the ITT population and will be included in the safety population.

Acceptance Criteria: Endpoint success at each timepoint is defined as test group cuff closure failure rate less than or equal to that of the reference group.

Statistical Analysis Method: A two-sided Fisher's Exact Test will compare (test versus reference) rate of dehiscence at each timepoint. Assessment of this endpoint is independent of primary study endpoint results.

Secondary Endpoint (2) Cuff healing (compared between test and reference groups), will be assessed (yes or no) by an independent surgeon at six weeks and six months.

Data collection: Surgeon visual assessment of cuff healing is limited to a single binary assessment ("healed" or "not healed"). Additional descriptive observations are included during data collection but are not used in comparative analysis. If the vaginal cuff is determined not to be healed, then failure of this study endpoint will be indicated. If additional surgical intervention is necessary, follow-up will restart following the new procedure date. In this circumstance the new follow-up schedule will be included in the evaluation of remaining efficacy endpoints in the ITT population and will be included in the safety population.

Acceptance Criteria: Endpoint success is defined as a test group cuff healing failure rate less than or equal to that of the reference group.

Statistical Analysis Method: A two-sided Fisher's Exact Test will compare (test versus reference) rate of visually assessed, failed cuff healing at each post-operative timepoint. Assessment of this endpoint is independent of the primary safety endpoint.

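### Section 3.2(2) fills an ungradable cuff healing result with a closure grade, a different variable, and the next sentence can give the same woman the opposite result

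*Combined protocol and SAP*

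**What the plan says.** Section 3.2 treats closure and healing as two endpoints with different schedules. For closure: "Cuff closure will be assessed by an independent surgeon at one and six weeks, as well as at six months". For healing: "Vaginal cuff healing will be visually assessed by an independent surgeon at six weeks and six months".

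Healing has three possible entries: "Surgeon visual assessment will grade vaginal cuffs as healed or not healed, or the surgeon may indicate that it was not possible to determine". Two consecutive sentences deal with the third entry. The first is "In cases in which a surgeon is unable to assess cuff healing, the most recent successful evaluation of cuff closure will be used". The second is "If no prior evaluation has established cuff healing, the cuff will be assumed to have not healed yet".

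The closure endpoint, just above, has a parallel rule: "the most recent successful evaluation of cuff closure (including intra-operative evaluation) will be used". There the variable being filled and the variable used to fill it are the same.

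Section 9.4.4 sets the success criterion for healing: "Endpoint success is defined as a test group cuff healing failure rate less than or equal to that of the reference group". It sets the test as well: "A two-sided Fisher's Exact Test will compare (test versus reference) rate of visually assessed, failed cuff healing at each post-operative timepoint". It gives no rule for a cuff that cannot be graded. Section 9.4.10 deals with loss to follow-up and with rescue closures, not with a woman who attends and cannot be graded. The general denominator rule in section 9.4.1 gives way where something else is specified, and section 3.2 does specify something else.

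**The concern.** A closure grade says whether the cuff edges are together. The plan grades healing separately because it is a different question. A rule that fills one with the other can record a cuff as healed when nobody has judged it so. The sentence that follows points the other way, and the plan gives neither an order of precedence nor a mapping from closed to healed.

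Two consequences follow if the first sentence is applied literally. At six weeks, a woman who could be graded for neither closure nor healing would take her one-week closure grade. Section 8.1 puts that visit at 7 ± 3 days, inside the 14-day period that section 6.1.2 calls critical for wound healing. At six months, a woman graded closed but not healed at six weeks, and ungradable at six months, would become healed. A carried-over closure grade would then replace an observed failure.

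The success criterion is a bare numerical comparison of two small arms, so a single woman can decide it. Section 6.3 places database lock and unblinding after the last six-week visit. If the rule is still open then, the choice could be made with the arms known.

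**Working it through.** **Inputs.** Arm sizes of 39 test and 20 reference, a goal of 35 test subjects and 10% loss to follow-up (section 4.1). Two-sided 0.05 level (synopsis, Statistical Methods). Success criterion and Fisher's exact test (section 9.4.4). The documents give no expected number of ungradable women, so that number is an assumption, shown over a range.

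**The plan's own figure.** 35 / 0.90 = 38.9, rounded up to 39. Reference 39 / 2 = 19.5, rounded up to 20. Total 59. This agrees with the plan and is used only as the denominator below.

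**Step 1: the two sentences as decision rules.** I take a successful evaluation to mean one that could be completed. Sentence 1 can supply a healing success only if closed is coded as healed; the plan does not say so, but there is no other route.

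| Woman who cannot be graded for healing | Sentence 1 | Sentence 2 | Conflict |
|---|---|---|---|
| At six weeks; last closure grade closed; no earlier healed grade | healed | not healed | yes |
| At six weeks; last closure grade not closed; no earlier healed grade | not healed | not healed | no |
| At six months; closed but not healed at six weeks | healed | not healed | yes |
| At six months; closed and healed at six weeks | healed | default not triggered | no |

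Healing is first scheduled at six weeks and closure at one week. The first row is therefore the usual case for a woman ungradable at six weeks.

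**Step 2: size, by illustration.** Assume every graded woman is healed, and every ungradable woman was last graded closed with no earlier healed grade. Let u be the number ungradable in test and v in reference. Under sentence 1 the failure rates are always 0% vs 0%, p = 1, criterion met. Under sentence 2 they are u/39 and v/20:

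| u | v | Test | Reference | Fisher p | Criterion |
|---|---|---|---|---|---|
| 1 | 0 | 1/39 = 2.6% | 0% | 1.00 | not met |
| 2 | 0 | 2/39 = 5.1% | 0% | 0.54 | not met |
| 4 | 0 | 4/39 = 10.3% | 0% | 0.29 | not met |
| 7 | 0 | 7/39 = 17.9% | 0% | 0.083 | not met |
| 8 | 0 | 8/39 = 20.5% | 0% | 0.042 | not met |
| 1 | 1 | 2.6% | 1/20 = 5.0% | 1.00 | met |
| 2 | 1 | 5.1% | 5.0% | 1.00 | not met |
| 2 | 2 | 5.1% | 2/20 = 10.0% | 0.60 | met |
| 0 | 1 | 0% | 5.0% | 0.34 | met |

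**Step 3: after losses.** With arms of 35 and 18 (20 × 0.9), one ungradable test woman and none in reference gives 1/35 = 2.9% vs 0%, not met. Fisher's p again first falls below 0.05 at eight (8/35 = 22.9%, p = 0.040).

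**Step 4: the Fisher sentence.** The paragraph for the healing endpoint in section 3.2 says the test compares closure scores. The synopsis says healing scores, and section 9.4.4 says failed healing.

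**The case against.** The strongest reply is that the paragraph, read in order, gives one answer. A closure grade does not establish healing, so the second sentence acts as the fallback and the woman counts as not healed. On this view the word closure was copied from endpoint (1), and the Fisher slip in the same paragraph supports that. This is probably what was meant. It does not rescue the text, because a programmer who follows the first sentence as written would fill with closure and never reach the fallback.

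Several limits on the concern stand:

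- A reader might infer that every woman ungradable at six weeks changes from success to failure. She does not if her last closure grade was not closed, or if healing was already recorded, for example at an unscheduled visit, where the Schedule of Activities provides for a closure and healing assessment.
- A reader might infer that an intra-operative grade can be carried in as healed. The words allowing an intra-operative evaluation appear only under endpoint (1).
- A reader might infer that a one-week cuff is always what gets counted. Closure is also graded at six weeks, so if only healing is ungradable the latest closure grade is from that same visit.
- A reader might infer that Fisher's test will be run on the wrong variable. The synopsis and section 9.4.4 both state the comparison correctly, so this is a wording slip confined to section 3.2.

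The weight is also limited. The synopsis labels the secondary endpoints exploratory, sections 4.2 and 9.2 say they are not powered, and neither primary endpoint uses healing.

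**Conclusion.** The point holds within limits. Section 3.2(2) states a fill rule that uses the wrong variable and sits beside a default that can contradict it; no other section resolves this for a woman who attends but cannot be graded. The conflict depends on reading closed as healed. It affects women last graded closed with no earlier healed grade, including those closed but not healed at six weeks and ungradable at six months.

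The numerical criterion can turn on one woman: 0% vs 0% becomes 2.6% vs 0% if one test woman and no reference woman is ungradable and all others are healed. A reader might conclude that the documents show the result will be reversed. They do not: that depends on the unknown number of ungradable women in each arm, and with one in each the criterion is met under both rules. Statistical significance is hardly at issue, since about eight such test women and none in reference are needed before Fisher's p falls below 0.05. This is a modest correction to a secondary endpoint, worth making before unblinding.

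**What to change.** In section 3.2(2), make the first sentence carry forward the most recent completed evaluation of cuff healing instead of cuff closure. Keep the second sentence, so that a cuff for which healing was never established counts as not healed. In the Fisher sentence of the same paragraph, change closure scores to healing scores, to match the synopsis and section 9.4.4. Repeat the fill rule under secondary endpoint (2) in section 9.4.4, so that the analysis text carries it. Reporting the number of ungradable women by arm and visit, with a sensitivity analysis that leaves them out, would show whether the rule mattered.

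The cost is two word changes and one added sentence, plus one extra table if the sensitivity analysis is adopted. No visit, assessment, sample size or clinical rule changes.
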